## STATISTICAL ANALYSIS

**Endpoints:** *Primary endpoint:* Fecal BA excretion in obesity vs. health and the change from baseline with high fat/high calorie diet vs. low calorie diet. *Secondary endpoints:* (a) fecal individual BA and SCFA excretion; (b) fasting serum C4 and FGF19; (c) serum BA; and (d) serum fasting, peak and AUC postprandial FGF-19, GLP-1 and PYY.

**Statistical analysis:** The proposed analyses are based on analysis of covariance models, with the responses being each variable compared to baseline. The covariates to be considered include gender and BMI.

**Sample size:** In healthy volunteers, the normal value for fecal BA is  $957 \pm 185$  micromoles/48hours (SEM). The table below summarizes data for primary endpoint considering the mean difference between two groups (healthy vs. obesity) and difference between baseline to high fat vs. low fat diet in each group (healthy vs. obesity), n=8 per group; and estimates the effect size detectable with 80% power based on a two sample t-test at a two-sided  $\alpha$  level of 0.05. We will accrue 38 participants to achieve the above given n value, assuming a 20% dropout rate.

Response	Mean	SD	Predicted differences [% (absolute #)] n=8/group
Fecal BA, $\mu$ moles/48hours	957	185	1) Patient with obesity compared to health: 25% (258 $\mu$ moles/48h) 2) Baseline compared to high fat vs. low fat diet: 24% (233 $\mu$ moles/48h)

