**Experimental design:** We will screen up to 45 participants to accrue a total of 38 participants [ 14 individuals with normal weight (BMI 20-25), 24 individuals with obesity (BMI >30)] to compare bile acid pathway, key elements of the enterohepatic bile acid regulation and incretin pathway at three different metabolic stages: 1) at baseline, 2) on a 100 grams of fat diet, and 3) on a low calorie, low fat diet. Participants will be on each diet for 7 days prior to collection of samples; with one week on regular diet between the high fat/calorie diet and the low calorie diet. Fasting and postprandial blood samples will be used to analyze, metabolomics, PYY, GLP-1, FGF-19, C4, BA, and short-chain fatty acids (SCFA) on test days. Saliva sample will be collected for GI peptides and metabolomics. Visual analog scale (VAS) ratings of appetite and satiation will be recorded during the day (on the same days) every 15 minutes for the first 90 minutes, then every 30 minutes. On day 5 and 6 (48 hours), stool from every bowel movement will be collected for fecal BA, SCFA and microbiome. Participants will repeat the stool collection and above studies for a total of three times. On day 5 of 1st, 2nd and 4th week, participants will undergo a flexible sigmoidoscopy with biopsies.

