**Experimental design:** We screen up to 45 participants and will study a total of 38 participants[ 14 individuals with a normal weight (BMI 18.5-25), 24 individuals with obesity (BMI >30)] to compare bile acid pathway, key elements of the enterohepatic bile acid regulation and incretin pathway in obesity compare to health (normal weight) at three different metabolic stages: 1) at baseline, 2) on a 100 grams of fat diet, or 3) on a low calorie, low fat diet. Participants will be on each diet for one week prior to collection of samples; with one week on regular diet between the high fat/high calorie diet and the low calorie diet. Diet will be provided by the metabolic kitchen. Participants will present after an overnight fast to the CRTU on day 5 and day 7 for testing. On day 5 participants will undergo a flexible sigmoidoscopy procedure from which a biopsy will be obtained. A bowel cleansing with water enema will be given by a CRTU nurse before the procedure. On day 7, participants will consume their "scheduled meal" and blood samples will be collected at -15, 0, 15, 30, 45, 60, 90, 120, 150, 180, 210, 240, 300, 360 minutes. Fasting and postprandial blood samples will be used to analyze, metabolomics, PYY, GLP-1, FGF-19, C4, BA, and short-chain fatty acids (SCFA). Plasma will be collected to analyze EV. Fasting saliva sample will be collected for GI peptide and metabolomics. VAS ratings of appetite and satiation will be recorded during the day every 15 minutes for the first 90 minutes, then every 30 minutes. Prior to discharge from the CRTU, participants will meet with study staff to discuss the following week's diet. On day 5 and 6 (48 hours), stool from every bowel movement will be collected for fecal BA, SCFA and microbiome. Participants will repeat the studies for a total of three times.

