**Participants (Inclusion and exclusion criteria):** Through the use of a natural language processing tool and the electronic medical records, we have an established database of ~1000 patients with obesity and no other comorbidities who reside within ~100 miles, and have been evaluated at Mayo Clinic in Rochester, Minnesota. Many of them have participated in our previous studies. The specific inclusion criteria for aim 1a includes: individuals with normal weight (BMI 18.5-25), or obesity (BMI >30); these will be otherwise healthy individuals with no unstable psychiatric disease and not currently on treatment for cardiac, pulmonary, gastrointestinal, hepatic, renal, hematological, neurological, or endocrine disorders.

Days	Week 1							Week 2							Week 3							Week 4							
	0	1	2	3	4	5	6	7	1	2	3	4	5	6	7	1	2	3	4	5	6	7	1	2	3	4	5	6	7
Diet	Screen visit	Baseline							High calorie / High fat							Baseline							Low calorie / low fat						
Stool BA		X X							X X														X X						
C4-GI peptides		X							X							X													
Flex Sig		X							X														X						

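### The stated ANCOVA does not target the obesity-versus-health difference in fecal bile acids that the study was sized on, the role of BMI is left open, and the 80% power given for 233 does not hold.

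*Combined protocol and SAP*

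**What the plan says.** All of this is in the Statistical Analysis section unless noted.

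- **Primary endpoint:** "Fecal BA excretion in obesity vs. health and the change from baseline with high fat/high calorie diet vs. low calorie diet". The first half is a comparison of levels between groups. The second half is a change.
- **Analysis:** "The proposed analyses are based on analysis of covariance models, with the responses being each variable compared to baseline". The next sentence adds: "The covariates to be considered include gender and BMI". No group term is named, nor any stage at which the groups are compared, nor a model for the level.
- **Sizing:** the sample size paragraph covers both contrasts and "estimates the effect size detectable with 80% power based on a two sample t-test", two-sided α 0.05, n=8 per group. The table gives 258 µmol/48h for obesity versus health and 233 for the diet contrast, with 185 in the SD column. The text labels the same 185 an SEM.
- **Groups:** the Approach section enrols "individuals with normal weight (BMI 18.5-25), or obesity (BMI >30", so BMI defines the groups and leaves a gap between them. The Abstract gives the numbers: "14 individuals with normal weight (BMI 20-25), 24 individuals with obesity (BMI >30".
- **Repeated measures:** the Approach section says "Participants will repeat the studies for a total of three times", and the visit schedule shows the same people at baseline, on the high fat diet and on the low calorie diet.

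**The concern.** The study is sized on a difference in level between two groups, but the response in the only stated model is referred to baseline. At baseline such a response is zero by construction or undefined, so the model as worded cannot give the baseline group contrast. At the diet stages, a group term on change answers a different question: whether the groups respond differently to the diet. That is a valid question, but it is not the one sized at 258.

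The covariate list adds a second uncertainty. BMI determines group membership. If it is entered beside a group term, the two are nearly collinear and the group effect is estimated with much less precision. If it replaces the group term, that does not happen. The plan does not say which is meant.

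For diet, the data are paired within participant. No paired or repeated-measures model is named, and the sizing uses a test for independent groups.

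At stake is whether a true group difference of the planned size is tested by an analysis able to find it, and whether that analysis is fixed before the data are seen.

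**Working it through.** **Inputs from the document:** differences 258 and 233; spread 185; two-sided α 0.05; n=8 per group for sizing; 14 and 24 enrolled; 20% dropout. Completers: 14 × 0.8 = 11.2 and 24 × 0.8 = 19.2, taken as 11 and 19.

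**Assumptions, not in the document:** 185 is an SD except in step 5; the group shift of 258 is the same at every stage; within-person correlation r is 0 to 0.7; BMI is uniform on 18.5-25 in the normal-weight group and from 30 up to 35, 40, 42 or 50 in the obesity group.

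**1. The plan's own figures, n=8 per group.** The standard error is 185 × √(2/8) = 92.5.
- 258: 258/92.5 = 2.79. The normal approximation gives Φ(2.79 − 1.96) = 79.7%, so the stated 80% is reproduced this way. The named t-test (14 df) gives 73.7%.
- 233: 233/92.5 = 2.52. The normal approximation gives 71.2% and the t-test 64.9%. Neither is 80%.

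So the 258 came from a direct comparison of two group levels.

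**2. Direct comparison of baseline levels, 11 versus 19.** The standard error is 185 × √(1/11 + 1/19) = 70.1, and 258/70.1 = 3.68. With 28 df, power is 94.4%.

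**3. The stated response, 11 versus 19 (simulation).**
- Change score: the expected group difference is 258 − 258 = 0. It rejects about 5%, the α level.
- Change adjusted for the baseline value: the group coefficient is 258(1 − r).

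| r | coefficient | rejects |
|---|---|---|
| 0.3 | 181 | about 56% |
| 0.5 | 129 | about 39% |
| 0.7 | 77 | about 23% |

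**4. BMI in the level model, 11 versus 19.** Beside a group term, the noncentrality becomes 3.68/√VIF with 27 df, where VIF is the variance inflation of group given BMI. For example, VIF 12.4 gives 3.68/3.52 = 1.05.

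| Upper BMI, obesity group | VIF | power, BMI beside group | power, BMI in place of group |
|---|---|---|---|
| 35 | about 12 | 17-18% | about 92% |
| 40 | about 8 | about 25% | about 90% |
| 42 | about 7 | 28-29% | about 89% |
| 50 | about 5 | 37-38% | about 86% |

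With gender alone as covariate (assumed 50% women), power is 93.6%.

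**5. If 185 is an SEM.** Then SD = 185 × √(source n). The source n is not given. An assumed 8 gives SD 523 and direct power of 24% at 11 versus 19; an assumed 30 gives SD 1013 and about 10%.

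**6. Diet contrast of 233 as a paired test.** The SD of the difference is 185 × √(2(1 − r)). For example, at r = 0.5 it is 185, and 233/(185/√8) = 3.56 with 7 df gives 86%.

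| n | r = 0 | 0.3 | 0.5 | 0.7 |
|---|---|---|---|---|
| 8 | 58% | 73% | 86% | 97% |
| 11 | 76% | 89% | 96% | >99% |
| 19 | 96% | 99% | >99% | >99% |

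**The case against.** **A two-sample t-test is named, and for the group contrast too.** This is correct. A reader might infer that the primary group comparison has no test anywhere in the plan, and that would go too far. But the test appears only as the basis for the detectable difference. The declared analysis is the ANCOVA, and the two do not match.

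**BMI is only to be considered, and no group term is written.** This stands. A reader might infer that the plan commits itself to an adjustment that removes most of the power. The text does not support that: the loss needs BMI beside a group term. What remains is that a choice worth this much power is left open.

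**Nobody would run the baseline contrast on a response that is zero at baseline.** Probably true. The analysis sentence may describe only the change half of the endpoint, and a level comparison is clearly intended. The defect is that the level half has no stated model, not that a wrong test has been fixed. The 5% and the 56/39/23% show what the stated response would do under an assumed constant shift; they do not predict what the analyst will do.

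**Change from baseline is already within-participant.** This also stands: for diet, the contrast is named and the model is missing. It is a specification gap and costs little power at 19 completers. One sentence in the Approach section reads as baseline plus either diet, but the aim and the visit schedule put all participants through all three stages.

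**The 94% depends on 185 being an SD.** Correct, and the document contradicts itself on this. The fall from 94% cannot be quoted without that condition.

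**Conclusion.** The point holds as a mismatch and an ambiguity in a primary analysis that should be settled in the text. The stated response does not target the 258 that the study was sized on. Taken as a change score it rejects at about the 5% level under a constant shift; adjusted for baseline it estimates only 258(1 − r). BMI beside a group term would cut power for 258 at 11 versus 19 completers from 94% to about 17-38%. BMI in place of group would not, and the plan does not choose.

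Separately, the 80% attached to 233 does not hold for the named test at n=8 per group, which gives 65%.

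The omission and the 65% follow from the document's own text and figures, the 65% with 185 read as an SD, as in the table. The other power figures rest also on the assumed BMI ranges, correlations, constant shift and completer numbers. If 185 is an SEM, the direct comparison is itself weak (about 24% to 10%), and that would be the larger problem.

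**What to change.** In the Statistical Analysis section:

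1. For obesity versus health, name the fecal bile acid level as the response, with a group term, adjusted for gender and not for BMI, and say that BMI is left out because it defines the groups. Either a comparison at baseline, or a mixed model over the three stages with a baseline contrast and a group-by-stage term, would do.
2. For diet, name a within-participant contrast of the high fat and low calorie stages. The group-by-stage term covers any difference in diet response between the groups.
3. Restate the sizing of 233: give either 65% for the two-sample t-test at n=8 per group, or a paired calculation with its assumed correlation stated.
4. Say whether 185 is an SD or an SEM. If it is an SEM, give the source n and recompute both contrasts.

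Items 1 to 3 need only wording and standard software, with no new data, visits or participants. Item 4 needs a check of the cited source. If 185 proves to be an SEM, the power statement will change materially.

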## ABSTRACT

[figure not shown]
**Introduction:** Bariatric surgery is associated with a 2-fold increase in the concentration of serum bile acids (BA). In rodents, BA delivered to the ileum induces weight loss and improves glucose homeostasis. These results are mainly mediated by the BA receptor, GPBAR1 (also known as TGR5). We recently identified a GPBAR1 gene variant associated with lower BMI and food intake. It is unknown whether the bile acid pathway is altered in obesity.

**Hypothesis:** Our central hypothesis is that the bile acid pathway (fasting serum BA, C4, FGF-19, fecal 48h BA excretion) is altered in obesity resulting in reductions in satiety-related hormones, such as FGF-19, PYY, or GLP-1. Therefore, there is a critical need to understand the role of BAs in food intake and body weight regulation in obesity compared to health.

**Aim:** Thus, we propose one specific aim: To characterize the bile acid pathway, key elements of the enterohepatic bile acid regulation and incretin pathway in obesity compared to health (normal weight) at three different metabolic stages: 1) at baseline, 2) stimulated by 100 grams of fat diet (standard, validated diet for testing bile acids) and 3) on a low calorie diet with <3% weight loss.

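### BMI is listed as an ANCOVA covariate for no particular contrast; entered raw beside group, it would turn obesity versus health into an extrapolation, because the groups share no BMI value

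*Combined protocol and SAP*

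**What the plan says.** The STATISTICAL ANALYSIS section of the combined protocol and SAP describes the model in two sentences: "The proposed analyses are based on analysis of covariance models, with the responses being each variable compared to baseline", then "The covariates to be considered include gender and BMI". It writes no group term, does not say whether BMI is continuous, categorical or centred, and ties BMI to no particular contrast.

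The primary endpoint in the same section is "Fecal BA excretion in obesity vs. health and the change from baseline with high fat/high calorie diet vs. low calorie diet". It therefore has a between-group part and a diet-change part. The aim in the ABSTRACT sets the comparison "in obesity compared to health (normal weight) at three different metabolic stages".

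Group membership is decided by BMI. The ABSTRACT plans "14 individuals with normal weight (BMI 20-25), 24 individuals with obesity (BMI >30"); the APPROACH plans "14 individuals with a normal weight (BMI 18.5-25), 24 individuals with obesity (BMI >30"); the common inclusion criteria in METHODS admit 18.5-25, or 30 and above. These versions differ at the edges, but under each of them the two ranges are disjoint and 25 to 30 is empty.

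**The concern.** A covariate adjustment compares groups at a common value of the covariate. Here no such value exists: the normal-weight group ends at 25 and the obesity group starts at 30. With untransformed BMI and group in one model, the group coefficient is found by extending a fitted BMI line across the gap. It no longer describes the difference between the people enrolled. Part or all of the difference that the study wants to measure is assigned to the BMI slope, and what remains is estimated imprecisely.

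Obesity versus health is part of the primary endpoint and the heart of the aim. Leaving the option open also allows a choice, once data are seen, between two models that answer different questions. The sample size is "based on a two sample t-test" with no covariates, so it makes no allowance for the loss.

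**Working it through.** **Inputs from the plan.** Spread 185 (labelled SEM in the sample-size text and SD in its table; taken as SD here), difference 258, two-sided alpha 0.05, 80% power, n=8 per group in the calculation, 14 and 24 accrued, 20% dropout. Evaluable: 14 × 0.8 = 11.2 and 24 × 0.8 = 19.2, so 11 and 19.

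**Assumed, because the documents give no BMI distribution or upper limit.** BMI uniform on 18.5-25 in health, and on 30 to 35, 40 or 50 in obesity.

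**1. The plan's own figure.** Detectable difference at n=8 per group, normal approximation: 185 × (1.960 + 0.842) × √(2/8) = 259. This reproduces the stated 258 (power 79.7%). An exact t calculation gives 73.7%. Neither includes BMI.

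**2. Standard error without BMI, 11 versus 19.** 185 × √(1/11 + 1/19) = 70.1. Power for 258 is 94%, or 93% in simulation with gender also in the model.

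**3. Standard error with raw BMI beside group.** The variance is multiplied by VIF = 1/(1 − r²), where r is the group-BMI correlation. Equivalently, VIF = 1 + (between-group sum of squares of BMI)/(within-group sum of squares). Between = (11 × 19/30) × gap² = 6.967 × gap². Within = 10 × 6.5²/12 + 18 × width²/12 = 35.2 + 1.5 × width².

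| Upper BMI | Mean gap | Between | Within | VIF | SE multiplier | SE | Power for 258 |
|---|---|---|---|---|---|---|---|
| 35 | 10.75 | 805 | 72.7 | 12.1 | 3.5 | 243 | 17% |
| 40 | 13.25 | 1,223 | 185.2 | 7.6 | 2.8 | 193 | 25% |
| 50 | 18.25 | 2,320 | 635.2 | 4.7 | 2.2 | 151 | 38% |

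Power is from the noncentral t with 27 degrees of freedom and assumes a step difference between groups. Simulations with gender in the model agree: 16-18%, 23-25% and 36-37%. At the plan's 8 versus 8, the same calculation gives 11-18% with raw BMI, against 74% without.

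**4. If fecal bile acid is linear in BMI.** With mean a + b × BMI, a model holding both group and BMI leaves nothing for group, so the expected group coefficient is 0. Simulation at 14 versus 24 with upper limit 40 (b = 258/13.25 = 19.5 per BMI unit): the unadjusted difference averages 258 (SD 63), and the BMI-adjusted coefficient averages −2 (SD 173).

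**5. Between-group difference in change.** Assuming a group difference in change of 233 and an SD of change of 185, power is 88% with group and gender and 14-32% once raw BMI is added. The collinearity is the same.

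**6. Within-group diet change.** In the obesity group alone (n=19), the SE of the mean change is about 185/√19 = 42.4. In simulation it is 43 with or without BMI.

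**7. BMI centred within group.** The centred covariate has mean 0 in both groups, so it is uncorrelated with group and VIF = 1. Simulated estimates are 256-260 and step power is 93%.

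**The case against.** The strongest reply is that the plan does not contain the harmful model. Four things must coincide: BMI is used, it is raw and continuous, it stands beside a group term, and this happens in the obesity-versus-health analysis. The plan only says BMI will be considered. The sentence before speaks of responses relative to baseline, and the sample-size text describes "difference between baseline to high fat vs. low fat diet in each group (healthy vs. obesity"), which is a within-group comparison where BMI does no harm. BMI could also be the way obesity status itself enters the model. The only method named for the between-group mean difference is an unadjusted t-test, although it is named for planning.

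Much of this stands, and it makes the harm conditional. It does not close the gap. The plan does not confine the ANCOVA to within-group change. If it did, the baseline contrast would have no stated model, and a between-group comparison of change would still be exposed (step 5).

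The magnitude is also open to challenge. The BMI spreads are assumed, and 93% is not a figure from the plan. If 185 is an SEM (say from 8 subjects, so SD = 185 × √8 = 523), power is already 22-23% without BMI and 6-8% with it, and BMI would not be the deciding problem. The SE multiplier and the change in what is estimated do not depend on 185.

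Three stronger readings are tempting and are not supported. A reader might infer that the plan commits to adjusting the primary contrast for raw BMI; it does not. A reader might infer that the diet comparisons are compromised; within a group they are not. A reader might infer that the adjusted result would take the wrong sign; that needs a particular curved relation with BMI, and the documents give none.

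**Conclusion.** The point holds in conditional form and should be fixed, with medium confidence. The plan leaves a group-defining variable available as a covariate for a primary contrast between groups that do not overlap on it. The lack of overlap follows from eligibility and needs no assumption. If raw BMI is entered beside group, the group coefficient is an extrapolation: about 0 on average under a linear relation, and with an SE about 2 to 3.5 times larger under a step effect. The fall in power from about 93% to 16-37% is an illustration that rests on the assumed uniform BMI spreads, 11 versus 19 evaluable and 185 read as an SD. It is not a property of the plan as written. Within-group diet changes are not affected.

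**What to change.** Add to the statistical analysis paragraph:

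> The obesity-vs-health contrast, at baseline and in change from baseline, will be estimated with group and gender as terms; BMI will enter these models only centred within group. Raw BMI may be used in within-group diet-change analyses or in a separate exploratory dose-response model without the group term.

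The cost is two sentences of wording. No participants, visits or measurements are added, and BMI remains available wherever it is informative.

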## METHODS

**Participants:** Eligible subjects will be invited to participate by letter. All subjects will be given a verbal explanation of the study, provided time to read and study the written consent form and its information, given opportunities to ask questions and a copy of the consent form. Participants will be informed of their right to withdraw from the study at any time without prejudice to their clinical management now or in the future. Consent will be sought by one of the medical doctor investigators or the study coordinator, and consent will be documented by the participant's signature on the consent form. All recruitment or contact information will be approved by Mayo's Institutional Review Board.

The common inclusion criteria include:

- Age: 18-65 years.
- Gender: Men or women. Women of childbearing potential will have negative pregnancy tests within 48 hours of enrolment.
- BMI: 18.5-25, or  $\geq 30$

The common exclusion criteria include:

- a) History of abdominal surgery including cholecystectomy and other than appendectomy, Caesarian section or tubal ligation.
- b) Positive history of chronic gastrointestinal diseases, or systemic disease that could affect gastrointestinal motility, or use of medications that may alter gastrointestinal motility, appetite or absorption, e.g., orlistat, phentermine.
- c) Significant untreated psychiatric dysfunction based upon screening with the Hospital Anxiety and Depression Inventory (HAD), a self-administered alcoholism screening test (AUDIT-C) and the Questionnaire on Eating and Weight Patterns (binge eating disorders and bulimia). If such a dysfunction is identified by a HAD score  $>11$  or difficulties with substance or eating disorders, the participant will be excluded and given a referral letter to his/her primary care doctor for further appraisal and follow-up. The AUDIT-C is a 3-item alcohol screening questionnaire that reliably identifies participants who are hazardous alcohol drinkers or have active alcohol use disorders. In men, a score of 4 or more is above the recommended limits will be reviewed by study personnel. In women, a score of 3 or more is above the recommended limits will be reviewed by study personnel. However when the points are above recommended limits, the provider will review the patient's alcohol intake over the past few months to confirm accuracy and determine study eligibility.

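### For the non-randomised obesity-versus-health contrast the plan names BMI, which nearly duplicates the group, as a covariate and does not name age; pre-specify age and sex instead

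*Combined protocol and SAP*

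**What the plan says.** The primary endpoint (STATISTICAL ANALYSIS, Endpoints) has a between-group part and a within-person part: "Fecal BA excretion in obesity vs. health and the change from baseline with high fat/high calorie diet vs. low calorie diet".

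The analysis paragraph in the same section reads: "The proposed analyses are based on analysis of covariance models, with the responses being each variable compared to baseline". On adjustment it adds only: "The covariates to be considered include gender and BMI".

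The groups are defined by BMI. The ABSTRACT gives "14 individuals with normal weight (BMI 20-25), 24 individuals with obesity (BMI >30"; APPROACH and METHODS put the lower limit for normal weight at 18.5, and METHODS admits a BMI of exactly 30. In every variant nobody between 25 and 30 can enter.

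The age criterion in METHODS is the same for both groups: "Age: 18-65 years". No section describes age matching, age strata, or a planned comparison or adjustment for age.

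For the obesity group, APPROACH (Participants) points to a recruitment source: "we have an established database of ~1000 patients with obesity and no other comorbidities". No comparable source is described for the normal-weight group.

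**The concern.** The obesity-versus-health contrast is observational. If the groups differ in age and fecal bile acid (BA) varies with age, part of the age effect will be reported as an obesity effect. Recruiting one group largely from a clinical database and the other from an unstated source is a plausible way for such a difference to arise.

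BMI does not help. Beside a group factor defined by BMI, it competes with group for the same information. The adjusted group difference is then a comparison at one common BMI, and any such value lies outside the BMI range of at least one group. The estimate relies on extrapolation and becomes very imprecise. The plan thus names a covariate that can absorb the effect of interest and does not name a cheap one that could protect it.

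This affects the baseline group contrast and any group difference in change. It does not affect change within a person between diets, because each person's age is the same on both.

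**Working it through.** **Inputs from STATISTICAL ANALYSIS.** Mean fecal BA 957 and spread 185 µmol/48h (labelled SD in the table, SEM in the text); design difference 258 µmol/48h with n=8 per group; 80% power; two-sided alpha 0.05; 20% dropout. Enrolment is 14 and 24, so expected completers are 14 × 0.8 = 11.2 and 24 × 0.8 = 19.2, taken as 11 and 19.

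**Assumptions, because the documents are silent.** The correlation r between age and fecal BA, the age gap between groups, and the spread of age and BMI.

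**1. The plan's own figure.** The normal approximation gives (1.960 + 0.842) × 185 × √(2/8) = 259, against 258 stated, so 258 rests on 185 being an SD. The exact two-sample t-test gives 279 at n=8 per group. With 11 and 19 completers the exact value is 203. None of these calculations includes a covariate.

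**2. BMI beside group.** Assume BMI is uniform on 18.5-25 and on 30-45.
- Group means: 21.75 and 37.5, a difference of 15.75.
- Within-group variances: 6.5²/12 = 3.52 and 15²/12 = 18.75. Pooled: (11 × 3.52 + 19 × 18.75)/30 = 13.17.
- Between-group variance: (11 × 19/30²) × 15.75² = 0.232 × 248.1 = 57.6.
- Variance inflation of the group contrast: 1 + 57.6/13.17 = 5.4. Standard error: × √5.4 = 2.3.

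If BMI explains nothing within groups, the detectable difference of 203 becomes about 203 × 2.3 = 467, well above 258. A wider BMI spread in the obesity group would reduce the inflation and a narrower one would increase it.

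**3. How far apart ages could be.** If ages are uniform on 18-65, the SD is 47/√12 = 13.6 years. If both groups come from one source, the 95% chance range for the mean age gap at 11 versus 19 is ±1.96 × √(1/11 + 1/19) = ±0.74 SD, about ±10 years. Different sources could widen it.

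**4. Bias without age adjustment.** Bias = r × gap in SD units × 185. The last column is the chance of a significant result at 11 versus 19 when there is no obesity effect, given that gap.

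| r | Age gap (SD) | Bias (µmol/48h) | % of 258 | False-positive rate |
|---|---|---|---|---|
| 0 | any | 0 | 0 | 5% |
| 0.1 | 0.5 | 9 | 4 | 5.2% |
| 0.3 | 0.5 | 28 | 11 | 6.7% |
| 0.3 | 1.0 | 56 | 22 | 11.9% |
| 0.5 | 1.0 | 93 | 36 | 24.7% |

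The rates are conditional on the gap. If both groups share one age distribution, the unadjusted test keeps its 5% over repeated samples, and adjustment mainly improves precision. A systematic recruitment difference is what produces lasting bias.

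**5. Cost of adding age.** If age is unrelated to fecal BA, the standard error of the group contrast is multiplied by √(1 + 0.232 × d²), with d the age gap in SD: 1.00 at d=0, 1.03 at 0.5, 1.11 at 1.0 and 1.13 at 1.1. Detectable differences at 11 versus 19, against 203 without age:

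| r | Gap 0 | Gap 0.5 SD | Gap 1 SD |
|---|---|---|---|
| 0 | 204 | 210 | 226 |
| 0.3 | 194 | 200 | 216 |
| 0.5 | 176 | 181 | 196 |

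All remain below 258.

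**The case against.** - **The covariate wording is open.** A reader might infer that the plan rejects age, or commits to a model with both group and BMI. It does neither. It lists candidates, excludes nothing, and does not say whether BMI would enter beside group or in its place. This stands. It limits the point to pre-specification, but it also leaves covariates to be chosen after the data are seen, in a study with 38 participants and many endpoints.
- **No age effect is documented.** A reader might infer that the contrast is in fact confounded. The documents give neither an age-fecal BA association nor an age distribution, so the bias may be zero. The absence of matching is likewise read from silence.
- **Larger biases can be constructed.** A change of 1% of 957 per year with a 15-year gap gives 9.57 × 15 = 144, or 56% of 258. That slope implies r = 9.57 × 13.6/185 = 0.70, and the gap is 15/13.6 = 1.1 SD, beyond the chance range above. Nothing in the documents supports it.
- **Eligibility already narrows confounding.** Entry is restricted to people without treated organ disease, chronic gastrointestinal disease or cholecystectomy, and with very little medication. This removes some age-linked routes, but not age itself.
- **The scope is limited.** A reader might treat the central hypothesis as a fecal BA difference alone, or think the diet comparisons are confounded too. The hypothesis covers the whole bile acid pathway; fecal BA is the primary endpoint, and its within-person part is not confounded by age.
- **The study is exploratory.** The ABSTRACT presents it as leading to later hypothesis-testing work. That lowers the stakes, but does not make BMI a useful covariate beside group.

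**Conclusion.** The concern holds as a risk that the plan does not control, not as a demonstrated bias. BMI is the wrong covariate beside a BMI-defined group: under the assumed spread it raises the variance of the contrast about 5-fold and can absorb or badly blur the obesity effect. Age is not named, although checking eligibility requires it for everyone.

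With SD 185, r from 0 to 0.5 and an age gap of up to 1 SD, the unadjusted bias is 0 to 93 µmol/48h, or 0 to 36% of 258, in either direction. These figures are for the baseline group contrast. Group differences in change are exposed in the same way, but the documents give no SD of change from which to size that bias. If 185 is an SEM, the true SD and the absolute bias are larger; the ratio of bias to a detectable difference computed from the same SD stays the same.

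**What to change.** In STATISTICAL ANALYSIS, replace the covariate sentence with a commitment along these lines: every obesity-versus-health comparison, whether of baseline level or of change from baseline, will include group, age (continuous) and sex; BMI will not be included as a covariate alongside group; age will be summarised by group. If a graded relation with BMI is of interest, fit it as a separate analysis.

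Inviting normal-weight participants so that their age and sex profile resembles the obesity group would help where practical, but is optional.

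The cost is a wording change and one degree of freedom, with no new data and no change in sample size. If age turns out to be unrelated to fecal BA, the standard error is about unchanged with balanced ages, about 3% larger at a 0.5 SD gap and about 11-13% larger at 1 to 1.1 SD. If age is related, precision may improve.
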